8.7 Study Group

The MDT panel members will be invited by the MDT Panel Chairs (Principal Investigators) and Coordinators to invite them to participate in the study. The panel members will be informed of the purpose of the study and time commitment needed to complete the study questionnaires.

8.8 Inclusion criteria

MDT meeting panel members, Coordinators and staff submitting MDT referrals will take part.

8.9 Exclusion criteria

There are no formal exclusion criteria.

9. Approaching participants to join the study

MDT panel members will be invited to participate in the study through their respective Principal Investigators, who act as the MDT chairs. A notification will be sent outlining the study's purpose and the One Referral intervention. While the effectiveness of this study relies on strong participation across the entire MDT, we acknowledge the importance of individual choice and informed consent. Therefore, each MDT member will be asked to provide individual informed consent to participate in the study. This approach ensures that ethical standards are maintained while also recognizing the collaborative nature of MDT work.

MDT members will be provided with a Participant Information Sheet detailing the study's objectives, procedures, potential risks and benefits, and their rights as research participants. They will also receive a Consent Form to document their informed agreement to participate.

Patient consent for the use of their data in the One Referral system, both for the purpose of the clinical treatment and for the research study will not be sought.

Clinical treatment: Personal data processing falls under the common law duty of confidentiality. When patients consent to investigation and treatment, this implies consent for care providers to process relevant information to facilitate their referral. Research study: No patient identifiable data will be accessed by external researchers.

Title: Salutare Dialogue for MDTs					
Authors	[name], [name], [name]	Ver.2		Date Authorised	22/01/2025

Internal NHS staff will observe MDT meetings to collect data on the MDT review duration, quality and outcomes. This data will be pseudonymized by NHS researchers.

10. Study Phases

The duration of each study phase is designed to align with the frequency of Multi-Disciplinary Team (MDT) meetings. This design ensures that an adequate number of MDT meetings are observed in each phase of the study. It is important to note that this study duration is indicative and may be subject to adjustment based on operational factors. For instance, if an MDT meeting is cancelled or rescheduled, the study period might be extended to ensure the target number of MDT meetings is observed in each phase. This flexibility in the study design allows for adaptation to the real-world clinical environment while maintaining the integrity of the research protocol.

10.1. Pre-intervention phase

Prospective review of complex cases discussed by the MDT will be completed.

10.2. Onboarding phase

MDT panel members will be registered on Salutare One Referral via their secure NHS accounts and provided with system training. The system training will consist of an instructional video demonstrating how to:

- Set up accounts via NHS account authentication
- Manage notification settings and configure profiles
- Set up a multi-disciplinary team
- Complete a referral form
- Send a referral form
- Report software issues and request assistance
- What to do in the event of system unavailability

All study participants will be required to complete the onboarding training.

Additionally, the Salutare support team provides assistance for any difficulties via email and an email chat feature. The support team is available during working hours from 8 am to 7 pm, with a response within the same working day. If issues cannot be resolved through the video and email support, a call will be scheduled to address the problem. The Salutare support team will also update instructional materials based on these interactions.

10.3. Intervention phase

The study intervention involves NHS staff interacting with the Salutare One Referral software. The interaction with the One Referral digital tool is classed as and evaluated as a 'digital health intervention'. The term, 'digital health intervention' - first used in the field of digital therapeutics to describe diagnosis, treatment and monitoring of health conditions using software and digital applications (FDA, 2022) - has more recently been expanded to cover the use of information and communication technology (ICT) in support of health and health-related fields, encompassing emerging areas such as the use of advanced computing sciences in big data, genomics, and artificial intelligence (WHO, 2019).

Title: Salutare Dialogue for MDTs					
Authors	[name], [name], [name]	Ver.2		Date Authorised	22/01/2025

Clinicians participating in the study will engage with the Salutare One Referral software by initiating patient referrals to the MDT through a structured workflow facilitated by the platform. Upon logging into Salutare One Referral using their secure NHS accounts, they are guided through the process of creating referrals, leveraging instructional videos and software-provided completion instructions.

The platform automatically populates essential patient data from the NHS Spine, including demographics. Doctors supplement this data by inputting specific clinical information pertinent to the referral, such as details about the reason for referral, recent test results, and any additional context that could aid in MDT decision-making.

Once a referral is submitted, MDT panel members utilise the platform to engage in virtual discussions with their colleagues as part of pre-MDT preparation. This collaborative environment allows them to share and review essential patient information, including medical histories, laboratory results, and radiology examinations, all seamlessly integrated into the platform. Salutare One Referral ensures that MDT panel members have comprehensive access to the necessary clinical data required for informed decision-making.

During MDT meetings facilitated by One Referral panel members actively contribute to discussions on patient cases, aided by the platform's capabilities to standardise and automate aspects of the referral and review process. As part of this process, doctors complete the risk scores of the respective MDTs including, for example, the ASA and SORT scores for each patient.

Following review completion, panel members export the finalised referrals as PDF documents compatible with Electronic Patient Record (EPR) systems, ensuring seamless integration of reviewed information back into clinical workflows. This integration supports continuity of patient care across healthcare settings and enhances overall efficiency in patient management.

10.4. Post intervention phase

Prospective review of complex cases discussed by the MDT will be completed.

11. Study Assessments

11.1 Baseline Assessment

The Baseline Assessment will be administered to the study participants on the first day of joining the study (Day 0). The Baseline Assessment survey will collect the user baseline information, such as their job role and MDT role, digital competency level and their views regarding the current safety, efficiency and effectiveness of the MDT.

11.2 Onboarding Assessment

The Onboarding Assessment will be administered at the end of the Onboarding Study Phase. This will include the System Usability Assessment (SUS) to collect participant feedback following completion of system training.

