8.3 The Study Evaluation Model

A Logic Model is used as a theory-based approach to explicitly articulate the underlying theory of change which shapes the desired outcomes and impacts achieved by the Salutare One Referral software as per the study hypothesis (Kaplan and Garrett, 2005; Hayes et al., 2011; Helitzer et al., 2010; Friedman & Wyatt 2006).

Title: Salutare Dialogue for MDTs					
Authors	[name], [name], [name]	Ver.2		Date Authorised	22/01/2025

How Salutare Dialogue can lead to better patient outcomes & NHS resource use

Key: Sources are in bold italic, eg *"Raine 2014"*

[figure not shown]

Figure 1: One Referral Logic Model

The chosen secondary endpoints are the observed clinical outputs. The study is a pilot project and therefore not powered to collect data on health outcomes mediated by the clinical outputs. Note: The patient communication module is currently not yet available and therefore will not be assessed in the present study. Observing the duration of MDT per-patient discussion time with and without One Referral contributes to understanding the software's influence on MDT efficiency. This endpoint sheds light on whether One Referral facilitates more concise and productive discussions among team members.

User questionnaires assessing MDT discussions' effectiveness and referral information completeness with and without One Referral provide further qualitative data on the software's impact. Lastly, evaluating MDT preparation time through user questionnaires offers insights into the software's efficiency in streamlining preparatory tasks.

The System Usability Score (SUS) (Brooke, 1996), the only validated tool used in this study, offers valuable insights into the acceptability of the One Referral software. SUS is a simple, widely used 10-statement survey that asks users to rate their level of agreement or disagreement to the 10 statements (half worded positively, half worded negatively) about the software under review.

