Usability research within the human-computer interaction field shows that user scores differ substantially over time, with users reporting more favourable scores as they expand their experience with the product (Mendoza and Novick, 2005; McLellan, 2012). Repeated observations of a group of users over time are recommended in order to follow up changes with respect to one or more evaluation variables., with initial use evaluation affording insights on 'discoverability' or 'learnability' and further evaluations elucidating true usability experiences.

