11.3 Intervention Assessment

An intervention assessment will be administered to collect participant views regarding the current safety, efficiency and effectiveness of the MDT.

Title: Salutare Dialogue for MDTs					
Authors	[name], [name], [name]	Ver.2		Date Authorised	22/01/2025

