11.4 Post-Study Assessment

Post-study assessment will be administered at the end of the post-study control period. The assessment will comprise the assessment of any safety, efficiency and effectiveness gains/losses associated with discontinuing the use of the Salutare One Referral Software.

12. Data collection from One Referral

KPI type	KPI collected
Engagement with One Referral	Number of users set up on One Referral
	Number of comments by users
	Number of referrals processed by MDTs

This study will employ a mixed reporting strategy to accurately represent different types of data collected throughout the study phases:

Time-Series Reporting:

Variables that can be meaningfully measured and reported for each MDT instance will be presented as a time series. This approach allows for the observation of trends over time and the potential identification of immediate and gradual effects of the Salutare One Referral software implementation. Examples include:

- Number of users engaging with the system per MDT
- MDT preparation time
- Duration of MDT per-patient discussion time
- Overall time for MDT meetings

Aggregate Reporting:

Some metrics are more appropriately reported as aggregate figures over the entire intervention period or for each study phase. Examples include:

- Percentage of cases re-presented to the MDT
- Mean or median time from referral submission to MDT decision implementation

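### Section 11 names the SUS only at the end of onboarding, the day before live use starts, although section 8.3 links true usability to later, repeated measurement

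*Protocol*

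**What the plan says.** Protocol section 8.1 gives the SUS, together with user questionnaires, as the means of assessing the primary endpoint. Section 8.3 describes it as "the only validated tool used in this study" and links it to acceptability of the software.

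Section 11 describes four assessments:

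- **11.1 Baseline:** role, digital competency and views of the current MDT.
- **11.2 Onboarding:** "This will include the System Usability Assessment (SUS) to collect participant feedback following completion of system training".
- **11.3 Intervention:** "An intervention assessment will be administered to collect participant views regarding the current safety, efficiency and effectiveness of the MDT".
- **11.4 Post-study:** "any safety, efficiency and effectiveness gains/losses associated with discontinuing the use of the Salutare One Referral Software".

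Only 11.2 names the SUS. On the training that precedes it, section 10.2 says: "The system training will consist of an instructional video demonstrating how to" carry out a list of set-up and referral tasks.

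Section 8.3, directly after introducing the SUS, reports that "user scores differ substantially over time, with users reporting more favourable scores as they expand their experience with the product". It adds that "Repeated observations of a group of users over time are recommended", and it separates initial evaluation, which shows learnability, from "further evaluations elucidating true usability experiences".

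**The concern.** The rationale and the schedule point in different directions. Section 8.3 treats an early score as a measure of how easily the software is learned and a later score as the measure of usability proper. Section 11 specifies only the early one.

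Panel discussion on the platform and its use in MDT meetings are described only for the intervention phase (section 10.3). The one specified SUS therefore comes before the activity that the study exists to evaluate. In-use evidence would then come from user questionnaires that the protocol itself does not count as validated, from the engagement counts in section 12 and from incident reports. None of these is a validated usability score after live use.

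The primary endpoint is meant to inform an amendment and expansion to further sites (8.1). Section 16.1 also lists evidence of user satisfaction within the standard that the pilot is designed to meet. A score taken before live MDT use is a weak basis for either purpose.

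**Working it through.** No power or precision calculation applies. The check is calendar arithmetic, followed by a comparison of passages.

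**Reproducing the schedule.** Inputs are the phase lengths in section 14 and the day numbers in section 13.

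| Phase | Complex case MDTs | Breast MDT (on hold) |
|---|---|---|
| Pre-intervention | 4 weeks: Days 1–28 | 2 weeks: Days 1–14 |
| Onboarding | 2 weeks: Days 29–42 | 2 weeks: Days 15–28 |
| Onboarding survey (SUS) | Day 42 | Day 28 |
| Intervention | 8 weeks: Days 43–98 | 4 weeks: Days 29–56 |
| Intervention survey | Day 98 | Day 56 |
| Post-intervention | 4 weeks: Days 99–126 | 2 weeks: Days 57–70 |
| Post-intervention survey | Day 126 | Day 70 |

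The phase lengths reproduce section 13 exactly. The gap from the SUS to the start of the intervention is 43 − 42 = 1 day (breast: 29 − 28 = 1 day).

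**What follows the only named SUS.**

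- Intervention days: 98 − 43 + 1 = 56 (breast: 56 − 29 + 1 = 28). All come after it.
- Meetings in that period, at the frequencies in section 6: RNOH every two weeks, 56/14 = 4; colorectal weekly, 56/7 = 8; about 12 in all (breast weekly, 28/7 = 4). This only restates the one-day gap in terms of use. The counts are approximate, because section 10 allows phases to be extended.
- Surveys naming the SUS: 1 of 4 (Days 0, 42, 98, 126).

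**Could another survey supply the in-use score?** Baseline cannot, because the pre-intervention period has no access to the software (section 1). The post-intervention survey comes 126 − 98 = 28 days after the intervention period ends, again without access. Of the surveys already scheduled, the Day 98 survey (Day 56 for breast) is the one that falls at the end of live use.

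**Exposure before the SUS.** It is not nil. Onboarding allows time for adjustment (section 1), 3–5 panel members take part in site beta testing (5.3), and end users take part in acceptance testing (5.2). The protocol does not describe any of these as use in live MDT meetings.

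**Consequence for analysis.** Section 8.5 plans mixed-effects models to compare usability scores. With one score per person, within-person change cannot be estimated. A comparison between MDTs or roles would remain possible.

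**Direction.** On the premise in 8.3 that scores improve with experience, the Day 42 score would tend to lie below an in-use score. By how much is unknown. The protocol gives no SUS standard deviation, and the RNOH respondent number is unclear (about 20 staff in section 1, about 10–11 meeting participants in section 6), so no precision figure is offered.

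**The case against.** The strongest reply is that the gap may be one of description. Sections 11.3 and 11.4 are short statements of purpose, not item lists, and the questionnaires are not part of the protocol. Section 8.1 does not limit the SUS to one occasion, and the text of 8.3 makes an intended repeat plausible. This stands as far as intent goes. It does not remove the problem: section 11 fixes which assessment carries the SUS, and nothing in it tells anyone to give it again.

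Four narrower points also stand in part:

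- Section 8.3 reports that repeated observation is recommended in usability research. It does not commit this study to a repeat. The conflict is between rationale and schedule, not a breach of a stated requirement.
- The comparison in 8.5 could be between groups, so a single time point does not by itself contradict that section.
- Section 16.1 asks for evidence of satisfaction, not for the SUS, and user questionnaires also serve the primary endpoint. In-use acceptability would be measured, but not with a validated tool.
- An early score would tend to understate usability, so it would not flatter the product. It would still answer a different question.

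Leaving the matter to a statistical analysis plan does not help, because the timing of an instrument is data collection.

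**Conclusion.** The concern holds and should be fixed before the intervention survey is issued. As section 11 is written, the only validated instrument in the study, which is also a primary-endpoint instrument, is given once, one day before the intervention period. There is no named SUS measurement during or after 56 intervention days (28 for the breast MDT). The protocol's own rationale would class that score as learnability.

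The conclusion rests on the surveys being built from section 11 as it stands. If the questionnaires already repeat the SUS at the end of the intervention, the defect reduces to a missing statement in 11.3. No numerical bias or loss of precision is claimed. The study can proceed, but without the change it would have no validated usability score reflecting live MDT use.

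**What to change.** 1. In section 11.3, state that the standard 10-item SUS is included in the intervention survey on Day 98 (Day 56 for the breast MDT if it goes ahead).
2. Name that score as the in-use SUS measure of acceptability, and the Day 42 (Day 28) score as the learnability measure. Report both, with the within-person change.
3. Use the same unmodified items at both times. Section 1 allows modifications to the SUS, and a change between occasions would weaken both the comparison and the claim that the tool is validated.
4. If a repeat is already intended, a sentence in 11.3 saying so is enough.

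The cost is ten items in a survey already being sent, one or two more minutes per respondent, and a short protocol amendment. No visit or survey is added.

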11.3 Intervention Assessment

An intervention assessment will be administered to collect participant views regarding the current safety, efficiency and effectiveness of the MDT.

Title: Salutare Dialogue for MDTs					
Authors	[name], [name], [name]	Ver.2		Date Authorised	22/01/2025

11.4 Post-Study Assessment

Post-study assessment will be administered at the end of the post-study control period. The assessment will comprise the assessment of any safety, efficiency and effectiveness gains/losses associated with discontinuing the use of the Salutare One Referral Software.

12. Data collection from One Referral

KPI type	KPI collected
Engagement with One Referral	Number of users set up on One Referral
	Number of comments by users
	Number of referrals processed by MDTs

This study will employ a mixed reporting strategy to accurately represent different types of data collected throughout the study phases:

Time-Series Reporting:

Variables that can be meaningfully measured and reported for each MDT instance will be presented as a time series. This approach allows for the observation of trends over time and the potential identification of immediate and gradual effects of the Salutare One Referral software implementation. Examples include:

- Number of users engaging with the system per MDT
- MDT preparation time
- Duration of MDT per-patient discussion time
- Overall time for MDT meetings

Aggregate Reporting:

Some metrics are more appropriately reported as aggregate figures over the entire intervention period or for each study phase. Examples include:

- Percentage of cases re-presented to the MDT
- Mean or median time from referral submission to MDT decision implementation

Where possible and informative, we will provide both time-series and aggregate data. For instance, while the percentage of re-presented cases will be reported as an aggregate figure, we may also track the absolute number of re-presentations per MDT meeting as a time series to identify any trends. This multi-faceted approach to data reporting significantly strengthens the study design and allows for a more comprehensive evaluation of the Salutare One Referral software's impact. By incorporating time-series data where applicable, we observe learning effects, showing how users' proficiency evolves throughout the intervention period, while also allowing us to detect any fatigue effects or declining engagement over time. Regular data collection helps us assess the Hawthorne effect, determining whether participants' behaviour changes due to being observed and if this effect diminishes. Furthermore, the post-intervention phase data will reveal any carryover effects, indicating whether the software's impact persists after its use is discontinued (Friedman, Wyatt & Ash, 2022).

Title: Salutare Dialogue for MDTs					
Authors	[name], [name], [name]	Ver.2		Date Authorised	22/01/2025

13. Schedule of interventions and assessments

Complex case MDTs (Stanmore Anaesthetics and Royal Free Colorectal Cancer)

	Day 0	Day 1 - 28	Day 29 - 42	Day 42	Day 43 - 98	Day 98	Day 99 - 126	Day 126
Baseline survey	x							
Pre-intervention period		x						
Onboarding period			x					
Onboarding survey				x				
Intervention period					x			
Intervention survey						x		
Post-intervention period							x	
Post-intervention survey								x

High-volume MDTs (Breast Cancer)

	Day 0	Day 1 - 14	Day 15 - 28	Day 28	Day 29 - 56	Day 56	Day 57 - 70	Day 70
Baseline survey	x							
Pre-intervention period		x						
Onboarding period			x					
Onboarding survey				x				
Intervention period					x			
Intervention survey						x		
Post-intervention period							x	
Post-intervention survey								x

High-volume MDTs (Breast Cancer)

	Day 0	Day 1 - 14	Day 15 - 28	Day 28	Day 29 - 56	Day 56	Day 57 - 70	Day 70
Baseline survey	x							

Pre-intervention period		x						
Onboarding period			x					
Onboarding survey				x				
Intervention period					x			
Intervention survey						x		
Post-intervention period							x	
Post-intervention survey								x

14. Study duration

The total duration of the study will depend on the frequency of MDT meetings and the number of cases discussed.

- Stanmore Anaesthetics MDT and Royal Free Colorectal Cancer MDT: The study duration will be approximately 18 weeks (4-week pre-intervention period, 2-week onboarding period, 8-week intervention period, 4-week post-intervention period)
- Royal Free Breast Cancer MDT: The study duration will be approximately 10 weeks (2-week pre-intervention period, 2-week onboarding period, 4-week intervention period, and a 2-week post-intervention period).

Additionally, 4 weeks are allowed to complete the study data collection.

15. Early Discontinuation/Withdrawal of Participants

This protocol ensures adherence to ethical considerations while respecting the operational dynamics of the study involving multidisciplinary teams, in accordance with UK Health Research Authority guidelines. Given that the collective participation of the whole MDT panel is required for the study to proceed, participants cannot withdraw individually without providing a reason. Therefore, a collective decision by the MDT is needed to pause or terminate the study, ensuring that the integrity and continuity of the research are maintained.

Study participants will be encouraged to contact the study team with any issues and questions and if they wish to opt out. All efforts will be made to resolve any issues. In the unlikely situation that issues cannot be resolved, the research team will discuss appropriate measures, such as allowing the panel members to submit referrals using the existing process.

Participants whose employment at the Participating Organisation is terminated during the study will be automatically withdrawn effective from their last day of employment, with no further data collected after employment ends or after the closure of their email account, whichever occurs first.

Title: Salutare Dialogue for MDTs								
Authors	[name], [name], [name]	Ver.2		Date Authorised	22/01/2025		Page 23 of 32	

While every effort has been made to ensure the safety and efficacy of the Salutare One Referral software, it is important to outline potential adverse events that might necessitate early termination of the study. The MDT panel, in consultation with the study team, may discuss early study termination if any of the following events occur:

- Cybersecurity Incidents: Any breach or attempted breach of the system that compromises or potentially compromises patient data or system integrity.
- Severe Usability Problems: Persistent issues that significantly impair the MDT's ability to function effectively, such as consistent system crashes during meetings or inability to access critical patient information.
- Unexpected Patient Safety Issues or Near Misses: Any incidents or near misses that could potentially harm patients due to software malfunction, such as incorrect display of patient data or loss of critical medical information.
- Prolonged System Malfunction or Outage: Extended periods of system unavailability that disrupt MDT operations and patient care pathways.
- Significant Negative Impact on MDT Efficiency: If the software consistently leads to prolonged MDT sessions or increased workload that cannot be attributed to a learning curve.
- Unresolved Critical Bugs: The discovery of critical software bugs that cannot be promptly resolved and pose risks to MDT operations or patient safety.
- Ethical Concerns: Any unforeseen ethical issues that arise during the course of the study.

If any of these events occur, they will be promptly reported to the study's Chief Investigator, Principal Investigator and Sponsor. The severity and impact of the event will be assessed, and a decision regarding study continuation will be made in consultation with the MDT panel, ethics committee, and other relevant stakeholders. The wellbeing of patients and MDT members will always be the paramount consideration in any such decision.

16 Legal and Regulatory Requirements

